Appendix A
 - Wisconsin Brief Pain Questionnaire (BPQ)
Appendix B
 - Collett-Lester Fear of Death Scale
Appendix C
 - Tandem VR Interview Guide
Appendix D
 - Tandem VR Intake Form
Appendix E

All data will be stored in a HIPAA secure Box folder.

5. Data Management

Our study includes participant data collection with information obtained from the PHI within the EHR by the **Prisma Social Workers (PSW)** and/or the **Prisma Research Team Members (PRT)**. These team members are employees of Prisma Health System. The following quantitative and qualitative data (for which we have participant consent to share in de-identified form) will be collected as part of the project and will be de-identified before sharing with the Clemson research team.

Data Elements

Demographics. Demographic data that will be collected by the PRR/PRT from the patient will include year of birth, gender, racial group, ethnicity, primary diagnosis for enrollment into hospice, length of time in hospice care services. The PRR/PRT will collect how long the informal caregiver has been serving in the role.

Qualitative Data. Qualitative field notes from dyad encounters with interventions and transcribed responses to semi-structured follow-up questions will be stored on the EXCEL spreadsheet provided.

- Tell us about your experience in Tandem VR?
- What was it like being together in the Tandem VR experience?
- Was there anything about the Tandem VR experience that helped you?
- Was there anything about the Tandem VR experience you feel could be improved?
- Were there any unusual sensations such as dizziness, lightheadedness, or disorientation while you were in the Tandem VR experience? If so, please explain.

Quantitative Data. Patient-level data retrieved from the EHR by the PRR/PRT will be de-identified before sharing with the Clemson team. We will collect pre- and post-assessments of the intervention on paper surveys from the patient and caregiver. These assessments will be de-identified, stored in a locked cabinet, and will include the following instruments:

- McGill Quality of Life Questionnaire-E (MQOL-E)
- Wisconsin Brief Pain Questionnaire (BPQ)
- Collett-Lester Fear of Death Scale
- VR Tandem Intake VR Request form

Types of data

The EXCEL spreadsheet below contains the specific patient-level variable listing that will be collected by the PRR/PRT. The PRR/PRT will establish the guideline for managing confidentiality of the single data file containing the participant names and study ID numbers. Time Frame: The PRR/PRT will collect these data points prior to the participant's completion of the research intervention and following the intervention. These data will allow the researchers to determine the effectiveness of the intervention.

EXCEL Spreadsheet. Patient level data retrieved from EHR by PRR/PRT

Patient's Information. Each patient's name will be transposed into a unique (random) study identification number by the PRR/PRT: year of birth, gender, racial group, ethnicity, primary diagnosis for enrollment into hospice, length of time in hospice care services.

Participant-level data. When participants give consent and are enrolled in the study, each will be assigned a unique (random) study identification number by the PRR/PRT. This ID number will be associated with all participant data that are collected, entered, and analyzed for the study. The link between participants' names and study ID numbers will be kept in a separate electronic file on the computer of the PRR/PRT PI on a password protected computer that is kept in locked office, ensuring that all data prepared for analysis are de-identified. Directly identifying information will never be maintained in the same files. All paper data (pre- post- intervention) will be stored in locked file cabinet that will be accessible only to research staff at the Prisma Health Hospice of the Foothills site. The paper data will only be labeled with the participant's study ID. During the active project period (while data are being collected, coded, and analyzed), data from participants will be entered into the data spreadsheet (included for review) by the PRR/PRT into the Clemson University's secure BOX storage (box.clemson.edu), which is a highly secure online file-sharing system.

Participants' study ID numbers will be associated with the data entered into BOX. Data will be downloaded from BOX for analysis onto password protected computers and saved only on secure Clemson University servers.

Patient-level data retrieved from EHR by the Tandem VR Team

All data to be used in the proposed study will be obtained from the PRR/PRT; only completely de-identified data will be logged into the EXCEL spreadsheet. Data collected by the Research Recruiters will occur in a secure location within the practice office location ([name]).

Types of data

The EXCEL Spreadsheet contains the specific variable list that will be used in the proposed study that will be collected by the Tandem VR Team. While the data involves human subjects, only completely de-identified data will be available and used in the proposed study. Secondary data use is expected to be limited to the specific variables listed in the excel spreadsheet.

Data sharing agreement

Data sharing will occur upon approval of the data management plan submitted to Prisma Health System.

Data repository/sharing/archiving

A long-term data sharing, and preservation plan will be used to store beyond the life of the project. The de-identified data will be deposited into the CLEMSON University secure BOX folder.

Roles and Responsibilities

PRR/PRT will be responsible for ensuring de-identified data are "active" (i.e., during data collection, coding, analysis, and publication phases of the project), and will be responsible for documenting and managing the data throughout the period of the research study.

Additional non-Prisma project personnel (Clemson researchers and undergraduate/graduate research assistants to be determined) will receive human subjects and data management training and will also be responsible for adhering to the data management plan described above. These additional project personnel will not have access to any PRISMA HEALTH electronic records.

PRT will develop study-specific protocols and will train all PRR handling identifiable data and de-identified data using protocols for naming, organizing, and sharing files and entering and downloading data. We will also develop a directory that lists all types of data and where they are stored and entered. For the CU team, we will designate the PI ([name]) to ensure that these protocols are followed, and documentation is maintained.

Data from this study will be stored in HIPAA compliant Box software. The Co-PIs, Co-Is, and the research assistants will have password protected access to the Box. All the information will be stored in an encrypted database. Electronic communication with outside collaborators will involve only unidentifiable information. Only the primary investigators and members of the research team that will contact the participants will have access to information linked to participant identifiers. Long-term plans for archiving data, samples, and other research products, and preservation of access will be undertaken by [name] and [name], RN, CHSE. The Co-PIs and Co-Is will maintain their parts of the data on the Box platform. The data will be retained at least three years after the conclusion of the study. Other electronic backup media and surveys will also be stored to ensure long-term availability of data. Should the Co-PI leave Prisma Health prior to completing the research, the data will be moved either to the relocating Co-PI's new institution, the Co-I's location, and/or to a site maintained by another member of the research community involved with the project. Data from this study will be retained to assist in development of future studies with larger patient populations, multi-site studies and also to aid in application for extramural funding.

7. Statistical Analysis

Differences in outcomes between pre and post intervention data will be statistically tested to determine if Tandem VR impacted primary outcomes. Independent sample t-tests will compare outcomes and changes in symptoms (i.e., pain). We will also triangulate quantitative and qualitative data outcomes with adjustments for sociodemographic characteristics to understand experiences for both the patient and informal caregiver following conclusion of the intervention.

V. ETHICAL CONSIDERATIONS

A. RISKS AND POTENTIAL BENEFITS TO PARTICIPANTS

1. Risks to Participants

The risks associated with participation in this study are no greater than those typically encountered in normal day activities. Certain aspects of the participant’s demographics will be collected for this study. Loss of privacy may lead to problems with insurability or social stigmatization. In terms of privacy, participant’s data and associated records will be kept in a secure encrypted, password-protected database. Confidentiality of participant information and study activities will also be emphasized to all research personnel. These risks are considered to be minimal and are addressed in the protocol and consent form.

Participants may develop VR-related symptoms such as motion sickness effect, nausea, and headache, often referred to as cybersickness. Measures will be taken to assess if any symptoms of cybersickness occur and discontinue the intervention immediately. The greatest risk is the possible release of your personal health information. The study records are considered confidential, but absolute confidentiality cannot be guaranteed. This study may result in presentations and publications, but steps will be taken to make sure patient data is deidentified. Some of the questions in the surveys/questionnaires are personal and may be upsetting to some participants. The study doctor or staff will be available to discuss these questions should you have a concern or problem. You do not have to answer any questions that you do not want to answer.

In case patients or patient caregivers become emotional during the Tandem VR experience, a Hospice care on-call social worker will be providing real-time and immediate counseling.

2. Potential Benefits to Participants

We expect that this study will demonstrate Tandem VR is an effective non-pharmacologic treatment for the management of physiological distress of patient-caregiver dyads; moreover, we expect Tandem VR will be feasibly and safely deployed in home settings. The expected outcomes from this study include reduction in pain, reduced fear of death and improved quality of life for participants. This intervention is also likely to show improved interactions between patient-caregiver dyads through the imagery used in Tandem VR. The outcomes from this study will be used

to optimize Tandem VR to user satisfaction. The results will also be used to inform and refine future design guidelines and practices for the implementation of Tandem VR for patient-caregiver dyads in the hospice home setting.

B. PARTICIPANT CONFIDENTIALITY AND PRIVACY

1. Participant Confidentiality

We will do everything we can to protect the participant's privacy. Collected data will be stored securely with access limited to the investigators. Paper forms will be kept in a double-locked storage and access to the storage will be restricted to the research team. Confidentiality of participant information and study activities will also be emphasized to all research personnel. Participant's identity will not be revealed in any publication that might result from this study. Limited demographic data will be collected. Data will be handled in a confidential manner to prevent loss of privacy. Electronic files will be stored in an encrypted and password protected database on a secure server. Only the primary investigators and members of the research team who contact the subjects will have access to information linked to subject identifiers.

2. Provisions to Protect the Privacy Interests of Participants

Under federal privacy laws, participants' study records cannot be used or released for research purposes unless the participant agrees. If the participant signs the consent form, he/she agrees to the use and release of health information. If not, the participant will not be able to participate in this study. Once health information has been released, federal privacy laws may no longer protect it from further release and use. The right to use health information for research purposes does not expire unless the participant withdraws agreement. The participant has the right to withdraw from the agreement at any time. This can be done by giving written notice to the study investigators. If the agreement is withdrawn, the participant will not be allowed to continue participation in this research study. However, the information that has already been collected will still be used and released as described above. The participant has the right to review health information that is created during participation in this study. After the study is completed, this information may be requested.

C. VULNERABLE POPULATIONS

N/A

D. CONSENT PROCESS

CONSENT TO PARTICIPATE IN A RESEARCH STUDY

**Tandem VR: Synchronized Nature-Based Experiences in Virtual Reality
for Hospice Patients and their Caregivers**

Study to be Conducted at: *Prisma Health Hospice of the Foothills*

[name]

[name]

Sponsor Name: *Prisma Health and Clemson University*

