Dyads have missed opportunities to engage in meaningful experiences, given the progressive nature of serious illnesses. Events such as family gathering for picnics or hiking in familiar outdoors spaces often hold valuable memories. The images, videos, and sounds can be personalized in nature-based VR experiences for use by each dyad. In Tandem VR, the dyad experiences memorable nature experiences concurrently. They can interact during the experience to recall precious moments or joyful times. Providing stimuli of sights and sounds, panoramic views with high resolution, and allowing interaction are key components in distraction techniques that can reduce the symptom burden during EOL phases. Evidence supports the use of distraction techniques through VR experiences, with one

study reporting a 30-50% reduction in pain scores.¹⁶ The uptake of Tandem VR by hospice teams offers a person-centered strategy for the patient’s wellbeing and the psychological needs of informal caregivers.

B. IMPORTANCE / JUSTIFICATION FOR STUDY

The primary objective of this study is to assess the impact of personalized nature-based Tandem VR experiences on QOL, pain, and fear of death in patient-caregiver dyads enrolled in hospice services.

Additionally, the study will determine the acceptance of personalized nature-based Tandem VR experiences by hospice teams as a non-pharmacological modality for addressing the needs of dyads.

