The primary aim of this study is to measure the impact on QOL using Tandem VR with patient-caregiver dyads transitioning to EOL. Our study will utilize an approach where participants will be asked to wear a VR HMD presenting Tandem VR content in a home setting. In addition to measuring the improvement in QOL, this study seeks to assess the efficacy of Tandem VR on patient-caregiver reported outcomes including pain and fear of death and assess the acceptability and safe use of Tandem VR in a home setting. The study will recruit 20+ patients from Prisma Health Hospice of the Foothills, who will be enrolled for treatment with Tandem VR. Research Recruiters will assist eligible patient-caregiver dyads in using the Tandem VR intervention in the comfort of their own home. The objective is to gather data on patients transitioning to EOL after being exposed to Tandem VR. The study will collect patient-caregiver reported outcomes including QOL, pain, and fear of death. The investigators will also assess acceptability and safety of Tandem VR at home. The investigators will also collect qualitative data following participants' Tandem VR experience to better understand the dyads' preferences, thoughts, and feelings about the intervention. Qualitative data will be garnered through audio recording in Otter, direct observation, and an interview. Outcomes will be measured before, and after the intervention. We expect that this study will demonstrate Tandem VR is an effective

non-pharmacologic treatment for improving QOL at EOL in patient-caregiver dyads; moreover, we expect Tandem VR will be acceptable and safely deployed in home settings.

IV. DESIGN & METHODS

A. STUDY DESIGN

Mixed-methods interventional study design: The study will recruit 20+ patient-caregiver dyads from Prisma Health Hospice of the Foothills enrolled in home care or at the hospice house. Once recruited, the dyads will be screened using the inclusion and exclusion criterion to ensure study eligibility. Dyads will also be offered the opportunity to participate in the Patient Advisory Council (PAC) to add further details on the experience in Tandem VR.

B. SETTING

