- Eligible participants will meet with the Research Recruiters and baseline data will be collected including demographics. Also, participants will complete Wisconsin Brief Pain Questionnaire (WBQP), Collett-Lester Fear of Death (FOD) scale, and McGill Quality of Life (QOL) scale directly before and after the intervention.
- Research recruiters will meet with participants in the home setting to assist dyads and implement the Tandem VR intervention.
- Upon completion of the intervention, Research Recruiters will collect the Tandem VR equipment and readminister the WBQP, FOD, QOL instruments, and semi-structured interviews.
- Consent from dyads will have been obtained by the Research Recruiters to participate in the Patient Advisory Council (PAC) to work with the researchers on understanding the experience.

Intervention

All procedures completed below will be done on one home visit.

The Tandem VR intervention will be carried out in the patient-caregiver dyad's home setting with the Research Recruiters implementing the experience. Each member of the dyad will initially complete the McGill Quality of Life Questionnaire-E (MQOL-E), Wisconsin Brief Pain Questionnaire (BPQ), and Collet-Lester Fear of Death (FOD) Scale prior to beginning the Tandem VR experience through an electronic medium.

Following completion of the pre-intervention forms, the dyads will be assisted by the Research Recruiter to don the VR HMD. The Research Recruiter will ensure safety for both participants while using the devices. The Research Recruiter will then initiate the Tandem VR experience using the iPad device to synchronize the nature-based scene for viewing. The duration of the experience will be 5-15 minutes.

Upon completion of the Tandem VR intervention, the HMD devices will be removed from the dyad participants. They will then complete the three instruments of the MQOL-E, BPQ, and FOD. Following the completion of the post-intervention documents, the Research Recruiter will conduct the semi-structured interview with the participants. Each participant will be asked the following questions to reflect on their experience:

- Tell us about your experience in Tandem VR?
- What was it like being together in the Tandem VR experience?
- Was there anything about the Tandem VR experience that helped you?
- Was there anything about the Tandem VR experience you feel could be improved?

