- Projected life expectancy of <6 months (required Hospice eligibility per Centers for Medicare/Medicaid)
- Cognitively intact (has sufficient judgment, planning, organization, self-control)

Exclusion Criteria:

- Have cognitive impairment that affects protocol participation. This will be done with the assistance of Research Recruiters (social workers, other hospice personnel recruited for the study, and the research team, such as the Research Assistants, PIs, and Co-Is) to assess eligibility.
- Have a condition that interferes with VR usage, including but not limited to seizures, facial injury precluding safe placement of headset.

- Have a prognosis of >6 months from the time enrollment.
- Have a prognosis of hours or actively dying at the time enrollment.
- Patients with motion sickness
- Patients with claustrophobia
- Patients with visual and hearing impairment
- Patients with inability to speak English.

****All patients in the dyad will continue their current standard of symptom management throughout the study of 8-16 weeks****

2. Study Endpoints

For each dyad, the study will end after 1 use of the intervention. Dyads will be recruited to participate in the PAC extending time for a period of 8 weeks where they will meet with researchers to discuss the experience. We anticipate the total duration of the study to be approximately 12 months following which all the compiled data will be analyzed and published.

3. Outcome Measures/Data

Primary outcomes

1. Well-being will be measured upon the patient's enrollment in the study and post-intervention with the McGill Quality of Life Questionnaire-E (MQOL-E).
This assesses eight important life domains: cognition, healthcare, environment, feeling like a burden, and their relationships with physical, psychological, social, and existential/spiritual domains. The 20-item questionnaire uses a 0-10 response scale and is used internationally by hospice teams to assess QOL.
2. Change in pain interference as assessed with the Wisconsin Brief Pain Questionnaire (BPQ) [Time Frame: Pre-Intervention(baseline), Post-intervention]
Pain will be assessed with the Brief Pain Inventory (BPI). Patients will rate their pain from 0=no pain to 10=worst pain imaginable in response to items such as "average pain," "worst pain" and "least pain" over the last 7 days and "pain right now". An average of the responses to these items is used to create a single pain severity score.

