3. Change in perception of fear of death with the Collett-Lester Fear of Death Scale [Time Frame: Pre-Intervention(baseline), Post-intervention]
4. Open-ended questions will be asked to determine the perceived benefit and value of the Tandem VR post-intervention with patient-caregiver dyads.

Secondary Outcomes

Follow-up semi-structured interviews with the hospice team and Research Recruiters will provide valuable information about the likelihood of integrating this intervention as a treatment modality for future dyads.

4. Data Collection Methods and Instruments Used

In this study, demographic data will be collected from all the participants. Demographic data will include age, sex, and race which will be used for secondary data analysis. In addition, EPIC EMR chart review would be used to collect demographic data from all the participants. In addition, we will also collect the medical record number (MRN), type of diagnosis, and life expectancy. Patient reported outcomes (PROs) will be measured using standardized symptoms assessment tools per study protocol. Standardized symptom assessment tools used in this study will include:

- McGill Quality of Life Questionnaire-E (MQOL-E)
 - Wisconsin Brief Pain Questionnaire (BPQ)
 - Collett-Lester Fear of Death Scale
 - Tandem VR Interview Guide
 - Tandem VR Intake Form
-
- (McGill Quality of Life Questionnaire-E (MQOL-E)
http://www.npcrc.org/files/news/mcgill_quality_of_life.pdf

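### The protocol names independent-samples t-tests for before-and-after scores from the same people, contradicts itself on the pain outcome, and does not settle whether quality of life alone is primary

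*Protocol*

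**What the plan says.** **Test.** Protocol IV.E.7 states "Differences in outcomes between pre and post intervention data will be statistically tested to determine if Tandem VR impacted primary outcomes". The next sentence reads "Independent sample t-tests will compare outcomes and changes in symptoms (i.e., pain"). No paired test, mixed model, significance level or multiplicity rule is given.

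**Data structure.** Under IV.E (Intervention), "Each member of the dyad will initially complete the McGill Quality of Life Questionnaire-E (MQOL-E"), together with the pain and fear of death scales. The same three instruments are repeated after the headset session, at one home visit. No control arm is described.

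**Pain outcome.** Protocol IV.E.3 and the SAP (Primary outcomes) head it "Change in pain interference as assessed with the Wisconsin Brief Pain Questionnaire (BPQ"). The text beneath names the Brief Pain Inventory (BPI) instead and ends "An average of the responses to these items is used to create a single pain severity score".

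**Primary outcome.** III.B says "The primary aim of this study is to measure the impact on QOL using Tandem VR with patient-caregiver dyads transitioning to EOL", and treats pain and fear of death as additional. II.B says "The primary objective of this study is to assess the impact of personalized nature-based Tandem VR experiences on QOL, pain, and fear of death". IV.E.3 and the SAP list all three scales as primary without ranking them.

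**SAP.** For the three scales it specifies means and standard deviations. It does not say whether these are of the separate pre and post scores or of the change.

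**The concern.** An independent-samples test treats the pre scores and post scores as coming from different people. Its standard error ignores the correlation between a person's two scores. When that correlation is positive and one group is analysed, the standard error is too large, and a real change can be missed. A study of about 20 dyads has little information to spare.

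The other two conflicts leave choices open until the data are in hand. Interference and severity are different constructs, here tied to different instruments, so two analysts could report different pain results and both claim to follow the plan. Whether the study has one primary scale or three determines what a positive result means and whether a multiplicity rule is needed.

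These points matter because the protocol does more than describe. It says the pre and post data will let the researchers judge effectiveness (IV.E.5), and it expects to show that the intervention works (III.B).

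**Working it through.** **Inputs from the documents.** Same people measured twice at one visit (IV.E); no comparison arm; at least 20 dyads (IV.D.4); Sample Size given as not applicable (IV.D.3). There is no stated power or detectable effect to reproduce.

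**Assumptions.** n = 20 complete pairs in one group, normal scores, equal pre and post SD (σ), two-sided 5%, pre-post correlation r = 0.25, 0.5, 0.7.

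**1. Interval width.** The independent test uses a standard error of σ√(2/n); the correct one is σ√(2(1−r)/n). The ratio of 95% CI widths is t(38)/(t(19)·√(1−r)) = 2.024/(2.093·√(1−r)):
- r = 0.25: 2.024/(2.093 × 0.866) = 1.12
- r = 0.5: 2.024/(2.093 × 0.707) = 1.37
- r = 0.7: 2.024/(2.093 × 0.548) = 1.77

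**2. Error and power.** Simulation, 400,000 replicates. The true change for power is 0.66 SD of change, which a paired t-test with 20 pairs detects with 80% power.

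| r | Actual error, independent | Actual error, paired | Power, independent | Power, paired |
|---|---|---|---|---|
| 0.25 | 2.5% | 5.0% | 73% | 80% |
| 0.5 | 0.7% | 5.0% | 54% | 80% |
| 0.7 | 0.1% | 5.0% | 26% | 80% |

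**3. If patients and caregivers are pooled as 40 independent people.** The true variance of the mean difference, divided by the variance the test assumes, is about (1−r)(1+ρ), where ρ is the within-dyad correlation. At r = 0.25 and ρ = 0.5 this is 0.75 × 1.5 = 1.125. The standard error is then too small, and simulated error is about 6.7 to 6.8%. At r = 0.5 and ρ = 0.5 it is 0.5 × 1.5 = 0.75, and the test is conservative again.

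**4. SAP summaries.** Illustration: SD 2 before and after, mean change 1, n = 20. The SD of change is 2√(2(1−r)), and the paired CI is 1 ± 2.093 × SD/√20.
- r = 0.25: SD 2.45, CI −0.15 to 2.15
- r = 0.7: SD 1.55, CI 0.27 to 1.73

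The same pre and post means and SDs fit both. If the SD of change is reported instead, the CI follows from it directly.

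**5. Multiplicity, if all three scales are primary and tested.** With independent outcomes, three valid 5% tests give 1 − 0.95³ = 14.3% chance of at least one false positive; simulation with outcome correlation 0.7 gives about 11%. With the named test at r = 0.25, 1 − 0.975³ = 7.3%. At r = 0.5, 1 − 0.993³ ≈ 2%.

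**6. Conflicts in the text.** Pain: heading is interference on the BPQ; text is an average severity score from the BPI. Primary status: III.B ranks quality of life first; II.B, IV.E.3 and the SAP do not.

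**The case against.** **The test sentence names no groups.** It could mean patients against caregivers, since the sentence after it mentions both. That reading is possible, and the power and width figures above would not apply to it. It does not rescue the plan: patient and caregiver scores are paired within dyad, so the test is still mismatched, and the promised pre-post test would then have no method.

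**The named test is not always conservative.** This stands. Step 3 shows that pooling with low pre-post correlation can push error above 5%. The loss-of-power figures apply to one group analysed separately.

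**The SAP may summarise change.** This stands too. Pain and fear of death are defined as changes, so the SDs may be of change. The precision point holds only if separate pre and post values are reported.

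**This is a small mixed-methods study with no success rule.** Fair, and it is why a descriptive route is offered in the fix. A reader might infer that the plan is also defective because it names no deciding group, gives no summary score for the quality of life and fear of death scales, and lists a qualitative item as primary: "Open-ended questions will be asked to determine the perceived benefit and value of the Tandem VR post-intervention with patient-caregiver dyads". The documents do not support going that far. Both dyad members are subjects of the study, and reporting each group separately serves that aim. The instruments sit in appendices whose contents could not be checked. The SAP already assigns the open-ended answers to themes and limits numerical summaries to the three scales.

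**Conclusion.** The concern holds in three parts: the test does not match paired data, the pain outcome contradicts itself, and the protocol is inconsistent on whether quality of life alone is primary.

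For one group of 20, the cost of the named test runs from modest at r = 0.25 (73% power instead of 80%) to severe at r = 0.7 (26%). The sample size, correlations, equal SDs and 5% level used here are assumptions. The pain and primary-outcome conflicts rest on the text alone.

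Three stronger readings should be resisted:
- **That the named test inflates false positives, or that it is always safe.** Neither is general; it depends on r and on whether dyad members are pooled.
- **That multiplicity matters only once paired tests are adopted.** At r = 0.25 the three named tests together already give 7.3% under independent outcomes.
- **That the SAP withdraws the protocol's tests.** It does not mention them either way.

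A paired analysis improves precision. Without a comparator it does not by itself establish effectiveness.

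**What to change.** 1. **Analysis (Protocol IV.E.7 and SAP, Primary outcomes).** Replace the independent-samples test with: within-person change (post minus pre), reported as mean, SD, 95% CI and paired t-test, two-sided 5%, for patients and caregivers separately and not pooled as independent people. If only description is intended, delete the testing sentences, report mean change with 95% CI, and call the results exploratory.
2. **Pain outcome (Protocol IV.E.3 and SAP).** Reconcile heading and text to one construct and one instrument before data are seen.
3. **Primary outcomes.** Reconcile III.B with II.B, IV.E.3 and the SAP: either quality of life alone or all three scales. If all three stay primary and are tested, apply Holm across them within each group, or label the results exploratory.

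**Cost.** A few sentences in each document and no new data, because IV.E.5 ties all of a participant's records to one study ID, so pre and post scores can be matched. The price of Holm is power. With 20 dyads the first step uses 0.05/3 = 0.0167, and power at 0.66 SD of change falls from 80% to about 63%. The change detectable with 80% power rises from 0.66 to 0.78 SD of change; about 27 dyads would restore 80% power at 0.66.
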